o First dose of the study intervention will be administered IV. A second dose is to be administered SC 4 to 6 hours after the IV dose on Day 1 followed by daily SC dose administration. A time window of \pm 1 hour is allowed for the daily SC study intervention administrations. Exception to this regimen: If a participant has received and tolerated a single dose of marketed caplacizumab intravenously (IV) for the presenting episode of iTTP within 4 hours prior to enrollment, the IV dose of study intervention at 0H will be skipped and the subcutaneous dose of caplacizumab due at 4-6H relative to the pre-study dose will be the first dose of study intervention. All subsequent doses will continue to follow the schedule as outlined in [Section 1.3.4](#) below. Please see [Section 1.3.4](#) below for details.

p For participants for whom TPE needs to be started only: TPE with plasma (eg, fresh frozen plasma, solvent detergent/viral-inactivated plasma, cryosupernatant) at 1 to 1.5 \times estimated plasma volume daily as of enrollment. See details in [Section 4.1](#).

q Recommend starting anti-CD20 antibody therapy (rituximab or biosimilar) once iTTP diagnosis is confirmed (ADAMTS13 level <10%) and is required if ADAMTS13 level remains <10%, 1 week after platelet count normalization or stop of TPE (if TPE was started).

s

1.3.3 Schedule of activities: Treatment and follow-up period (may include in-hospital & out-patient visits)

Study Period	Treatment Period (maximum 12 weeks)	Early Treatment Discontinuation Visit (\pm 3 days after last dose intake)	Follow-up Period ^l				
			FU Visit 7 days after last dosing (\pm 1 day)	Additional ^t FU Visit 14 days after last dosing (\pm 1 day)	Additional ^t FU Visit 21 days after last dosing (\pm 1 day)	FU visit 28 days after last dosing (\pm 1 day)	FU visit (EOS) 12 weeks after last dosing (\pm 3 days)
Study treatment administration							
IMP administration (daily) ^b	x						
Therapeutic plasma exchange (if needed) ^c	x						
Corticosteroids	x						
Anti-CD20 antibody therapy ^d	x						
eDiary (IMP administration info) ^e	x	x					
Safety and laboratory assessments							
Neurologic assessments ^f	x	x				x	x
GCS	x	x					x
Clinically significant TTP event	x	x	x	x	x	x	x
Bleeding assessment ^g	x	x	x	x	x	x	x
Physical examination	x	x	x	x	x	x	x
Vital signs ^h	x	x	x	x	x	x	x
12-lead ECG ⁱ	x	x				x	x
Adverse events	>						
Concomitant medication	>						
Clinical laboratory analyses ^j	x	x				x	x
Platelet count ^k	x	x	x	x	x	x	x

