Platelet count ^j	x ^g	x	x ^g	x	(x) ⁱ	x ^g	x	x	x ^g	x
Blood smear ^k	x ^g									
LDH ^l	x ^g	x	x ^g	x	(x) ⁱ	x ^g	x	x	x ^g	x
m	g					g			g	x

^a;GCS = Glasgow Coma Scale; IMP = investigational medicinal product; IV = intravenous; LDH = lactate dehydrogenase; PD = pharmacodynamics; PK = pharmacokinetics; RICO = ristocetin cofactor activity; SC = subcutaneous; TPE = therapeutic plasma exchange; TTP = thrombotic thrombocytopenic purpura; vWF = von Willebrand Factor.

^a Time (hour/minute) is expressed in reference to the first administration of IMP (T0H). In cases in which the participant has received and tolerated a dose of marketed caplacizumab for the presenting episode of iTPP within 4 hours prior to ICF signing, see footnote ^c below for interpretation of the time.

^b If TPE starts, blood draws during the TPE should be done only if possible.

- c If a participant has received and tolerated a dose of marketed caplacizumab IV for the presenting episode of iTTP within 4 hours prior to enrollment, the specific time of this dose should be documented, the IV dose of study intervention at 0H will be skipped and the subcutaneous dose of caplacizumab due at 4-6H after the pre-study dose, will be the first dose of study intervention. In these cases, all subsequent administrations of study intervention will continue to follow this schedule. The laboratory sampling schedule should remain unchanged (the time [hour/minute] for lab sampling is then expressed in reference to the time of enrollment).
- d First dose of the study intervention is to be administered IV. A second dose is to be administered SC 4 to 6 hours after the IV dose on Day 1 followed by daily SC dose administration. A time window of \pm 1 hour is allowed for the daily SC study intervention administrations. An exception to this is detailed in footnote [a](#).
- e For participants for whom TPE needs to be started only: TPE with plasma (eg, fresh frozen plasma, solvent detergent/viral-inactivated plasma, cryosupernatant) at 1 to $1.5 \times$ estimated plasma volume daily as of enrollment. See details in [Section 4.1](#).
- f Clinical laboratory analyses included hematology, coagulation parameters and clinical chemistry ([Section 10.2](#)).
- g Pre-cplacizumab dose.
- h Sample should be drawn before IMP administration and as close as possible to the IMP administration.
- i Optional assessments.

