- E 13. Participants who received an investigational drug, or device, other than caplacizumab, within 30 days of anticipated IMP administration or 5 half-lives of the previous investigational drug, whichever is longer. However, participants who have received any dose(s) of caplacizumab for the presenting episode of iTTP more than 4 hours before enrollment in Study EFC16521 are also excluded.

Diagnostic assessments

- E 14. Positive result on the Screening SARS-CoV-2 reverse transcription polymerase chain reaction (RT-PCR) test or on SARS-CoV-2 antigen test.

Other exclusions

- E 15. Sensitivity to any of the study interventions, or components thereof, or drug or other allergy that, in the opinion of the Investigator, contraindicates participation in the study.
- E 16. Individuals accommodated in an institution because of regulatory or legal order; prisoners or participants who are legally institutionalized.
- E 17. Participant not suitable for participation, whatever the reason, as judged by the Investigator, including medical or clinical conditions, or participants potentially at risk of noncompliance to study procedures.
- E 18. Participants are employees of the clinical study site or other individuals directly involved in the conduct of the study, or immediate family members of such individuals (in conjunction with section 1.61 of the ICH-GCP Ordinance E6).

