2 ANALYSIS POPULATIONS

The following populations for analyses are defined.

Table 3 - Populations for analyses

Population	Description
Screened	All participants who sign the informed consent form (ICF).
Enrolled	All participants from the screened population who met the eligibility criteria (ie, who are not screen failures). Participants who received caplacizumab and did not meet inclusion or met exclusion criteria are not enrolled, such as a participant with a confirmed alternate diagnosis.
Full Analysis Set (FAS)	All enrolled participants, who received at least 1 dose of the investigational medicinal product (IMP, ie, Caplacizumab). The FAS population will be used only for sensitivity analyses.
Modified ITT (mITT)	All enrolled participants who received at least 1 dose of IMP and with an evaluable primary endpoint. The mITT population will be the main efficacy analysis population. The primary endpoint is evaluable when the participant has an ADAMTS13 activity of <10% at baseline.
Safety	All enrolled participants who received at least 1 dose of IMP.
Pharmacokinetic (PK)	All enrolled and treated participants (safety population) with at least one post-baseline PK sample with adequate documentation of dosing and sampling dates and times.

Enrolled participants for whom it is unclear whether they took the IMP will be considered as exposed and will be included in the safety population.

To note that amended protocol 01 permits participants who have already received a dose of marketed caplacizumab for the presenting episode of iTTP within 4 hours prior to enrollment/ICF signing to enroll in the study. Consequently, participants exposed to a single dose of marketed caplacizumab within 4 hours prior to enrollment will be included in any analysis population.

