3 STATISTICAL ANALYSES

3.1 GENERAL CONSIDERATIONS

In general, continuous data will be summarized using the number of observations available, mean, standard deviation (SD), median, interquartile range (Q1, Q3), minimum, and maximum.

Categorical and ordinal data will be summarized using the count and percentage of participants.

No pre-specified success criterion or formal statistical hypothesis testing is planned. No statistical adjustment on interim analyses is planned.

When the notion of IMP is mentioned in the SAP, this refers to the study IMP.

The baseline value is defined as the last available value before the first dose of IMP, including participants who have received a dose of marketed caplacizumab for the presenting episode of iTP within 4 hours prior to enrollment. For participants enrolled but not treated with IMP, the baseline value is defined as the last available value before enrollment.

Efficacy endpoints derived from laboratory data (platelet count, lactate dehydrogenase [LDH], cardiac troponin I [cTnI], creatinine, ADAMTS13 activity) will be analyzed using central measurements, unless they are missing for a visit but the local value available, in which case the local value will be used under certain conditions (see [Section 5.4](#)). A central measurement will be considered missing if the recorded status is “NOT DONE” and there is a reason for this status or if status is “NOT PERFORMED”.

The observation period will be divided into 4 segments:

- The **pre-treatment period** is defined as the period up to the first caplacizumab administration (whatever marketed or study IMP).
- The **treatment-emergent (TE) period** is defined as the period from the first caplacizumab administration (whatever marketed or study IMP) up to the last caplacizumab administration **+ 28 days**. The TE period includes the following 2 periods:
 - The **on-treatment period** is defined as the period from the caplacizumab administration (whatever marketed or study IMP) to the last administration of caplacizumab.
 - The **residual treatment period** is defined as the period from the end of the on-treatment period to the end of the TE period.
- The **post TE period** is defined as the period from the end of the TE period.

The **overall study period** is defined as the time from the first caplacizumab administration (whatever marketed or study IMP) until the end of the study.

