3.2.3 Sensitivity analyses

As a sensitivity analysis, the primary endpoint will be analyzed on the FAS population ie, all enrolled participants who received at least 1 dose of the IMP.

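### Participants pre-dosed with marketed caplacizumab are counted from that dose but must get through to enrollment and a study dose first, so the earliest serious reactions, bleeds and TPE need may be understated

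*Protocol*

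**What the plan says.** **Entry.** The dosing exception in Protocol 1.3.2, footnote o, opens with the condition "If a participant has received and tolerated a single dose of marketed caplacizumab intravenously (IV) for the presenting episode of iTTP"; the dose may lie at most 4 hours before enrollment. Protocol 1.3.4, footnote c, is similar: "If a participant has received and tolerated a dose of marketed caplacizumab IV for the presenting episode of iTTP within 4 hours prior to enrollment". In that case the intravenous study dose is omitted, and the first study dose is the subcutaneous one due 4 to 6 hours after the marketed dose. Among the eligibility criteria (Protocol 5.2), E 13 sets only a time limit, excluding "participants who have received any dose(s) of caplacizumab for the presenting episode of iTTP more than 4 hours before enrollment". E 15 excludes "Sensitivity to any of the study interventions, or components thereof". E 05 (active bleeding), E 08 (immediate invasive procedures), E 09 (severe neurological or cardiac disease) and E 17 (investigator judgement) can also remove a candidate.

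**Populations.** In SAP Table 3, FAS, mITT and Safety all require enrollment and at least one dose of IMP. SAP 3.1 says that IMP means the study product. The note under Table 3 adds that "participants exposed to a single dose of marketed caplacizumab within 4 hours prior to enrollment will be included in any analysis population".

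**Clock.** SAP 3.1 defines the treatment-emergent period as "the period from the first caplacizumab administration (whatever marketed or study IMP) up to the last caplacizumab administration", plus 28 days. The on-treatment and overall study periods start at the same dose.

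**Sensitivity analyses.** SAP 3.2.3: "As a sensitivity analysis, the primary endpoint will be analyzed on the FAS population". SAP 3.3.1 does the same for the secondary efficacy endpoints. SAP 3.6.1.1 reports how many participants started with marketed product. The subgroup text (SAP 3.7.2) is not readable in the public version.

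**The concern.** Time at risk begins before membership is decided. In a participant whose first dose is study product, a severe reaction after that dose is a treatment-emergent event, and a deterioration leading to TPE is a primary-endpoint failure. In a candidate who had the marketed dose first, the same event can prevent enrollment or the study dose, and then it appears nowhere in the analysis. The pre-dosed participants who remain contribute a first dose and some hours of follow-up that are free of entry-blocking events by construction. This is the familiar immortal-time form of selection.

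Serious hypersensitivity is one of the two caplacizumab risks in Protocol Table 1, and the mitigation there names the first bolus. The trial has one arm, so no comparator shares the bias. The subset may not be negligible: the amendment history (Protocol 10.12.1) explains that many sites give the first dose when the disease is diagnosed clinically. No expected share or cap is stated.

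**Working it through.** **1. The plan's own figure.** Protocol 9.4 and SAP 4 give a 95% Wilson lower bound of 58% for n = 55 and a 70% responder rate, built from 85% remission and 18% TPE: 0.85 × (1 − 0.18) = 69.7%. With 39/55 = 0.709, z = 1.96 and z²/n = 0.0698:

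- centre = (0.7091 + 0.0349)/1.0698 = 0.695
- half-width = 1.96 × √(0.7091 × 0.2909/55 + 3.8415/(4 × 55²))/1.0698 = 0.117
- lower bound = 57.9%

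The 58% is reproduced when responders are rounded up to 39.

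**2. What is lost and what is kept.** The gap runs from the marketed dose to the first study dose, nominally 4 to 6 hours.

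- Lost: events in the gap that stop enrollment or the study dose.
- Kept: reactions that do not block entry. Protocol 8.3.1 collects AEs back to the first caplacizumab dose for those who sign the ICF, and SAP 3.1 makes them treatment-emergent.
- Recorded but not analysed: SAEs of consented screen failures (Protocol 5.4), who are outside the Safety population.
- Not affected: baseline (SAP 3.1), Table 7 study days (SAP 5.4) and the PCSA and ECG windows (SAP 3.6.3.1), which run from the study product.

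One ambiguity: read literally, the note under Table 3 could bring in an enrolled participant who never received a study dose. That would shorten the gap to the hours before enrollment but not close it.

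**3. First-dose reactions, worst case.** Let f be the pre-dosed share of about 61 treated participants and q the true first-dose reaction rate; both are assumptions. If every reaction blocked entry, the observed rate would be (1 − f)q. The chance of seeing none would rise from (1 − q)^61 to (1 − q)^(61(1 − f)).

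| | f = 0 | f = 20% | f = 40% | f = 60% |
|---|---|---|---|---|
| Observed rate, q = 5% | 5.0% | 4.0% | 3.0% | 2.0% |
| P(none), q = 5% | 4% | 8% | 15% | 29% |
| P(none), q = 2.8% | 18% | 25% | 35% | 50% |

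The 2.8% is the exact one-sided 95% upper limit for 0 anaphylactic reactions in 106 treated subjects (Protocol 2.3.1): 1 − 0.05^(1/106). Because tolerated reactions are kept, the table bounds the dilution from above.

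**4. Responder rate, by timing of TPE.** Assume that 10% to 40% of TPE starts fall in the first 4 hours and let a = 0.18 × that share. The TPE rate among selected participants is (0.18 − a)/(1 − a).

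- 10% share, f = 20%: 0.162/0.982 = 16.5%. Overall TPE is 0.8 × 18% + 0.2 × 16.5% = 17.7%, and responders are 0.85 × 0.823 = 70.0%.
- 40% share, f = 60%: 0.108/0.928 = 11.6%. Overall TPE is 0.4 × 18% + 0.6 × 11.6% = 14.2%, and responders are 0.85 × 0.858 = 72.9%.

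Against 69.7%, the overstatement is 0.3 to 3.2 points.

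**5. Responder rate, by candidates lost.** Let r be the share of pre-dosed candidates lost before the first study dose, and f now the pre-dosed share of the 55. Then lost = 55·f·r/(1 − r), with each one counted as needing TPE and as a non-responder. Start from 39/55 = 70.9% responders and 10/55 = 18.2% TPE.

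| f | r | Lost | Responders | Lower bound | TPE |
|---|---|---|---|---|---|
| 10% | 2% | 0.11 | 70.8% | 57.7% | 18.3% |
| 25% | 5% | 0.72 | 70.0% | 57.0% | 19.2% |
| 50% | 5% | 1.45 | 69.1% | 56.1% | 20.3% |
| 50% | 10% | 3.06 | 67.2% | 54.4% | 22.5% |
| 100% | 10% | 6.11 | 63.8% | 51.3% | 26.4% |

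**The case against.** A reader might infer that pre-dosed patients can join only if they tolerated the dose. The documents do not go that far. The word stands in dosing and timing footnotes, while E 13 and SAP 2 do not use it, and no criterion bars everyone who had a reaction. This objection stands and narrows the point, but selection does not depend on that word: E 05, E 08, E 09, E 15 and E 17 are applied after the marketed dose has been given.

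A reader might also infer that reactions before enrollment are never recorded. That is not so, since collection is tied to signing the ICF. Only patients who never consented are wholly unseen. The consented who fail screening are still outside the Safety tables.

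Three objections to the size also hold.

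- The readable SAP plans no first-dose or Day 1 rate. Bleeding and hypersensitivity are tabulated over up to 12 weeks of daily dosing plus 28 days, where one dose weighs little.
- Protocol 4.1 judges non-response after 24 hours and allows earlier TPE only for clinical deterioration. A 40% share of TPE starts within 4 hours has no source, and 4 hours is a maximum rather than a typical interval.
- There is no test or success criterion that a small shift could reverse.

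Finally, SAP 3.7.2 might already split by pre-dosing; the version history says that primary-endpoint subgroups are included. This cannot be checked, so the recommendation is conditional on it.

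**Conclusion.** The mechanism is in the documents and its direction favours the regimen; its size cannot be established. Early serious reactions, early bleeding and very early TPE need *may* be understated. The documents do not support saying that they *are* understated by a given amount.

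For the responder rate the effect is probably about 0 to 3 points. It reaches 3.7 points (70.9% to 67.2%) if half the participants were pre-dosed and 10% of pre-dosed candidates were lost. It reaches 7.1 points only if all were pre-dosed at that loss rate. The Wilson lower bound itself lies about 13 points below the estimate (70.9% against 57.9%).

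The safety side deserves more attention. A statement that no first-dose reactions were seen would carry less weight than its denominator suggests. Everything rests on assumed values of f, q, r and the timing of TPE. This is a cheap improvement to the SAP and does not threaten the main conclusion.

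**What to change.** - **SAP 3.6.2:** show treatment-emergent hypersensitivity, bleeding and Day 1 TEAEs by first-dose source (study product or marketed). Base any statement about first-dose reactions on participants whose first dose was study product.
- **SAP 3.2.3 and 3.3.1:** add a sensitivity analysis of the primary endpoint and of TPE need in mITT participants whose first caplacizumab dose was study product, unless SAP 3.7.2 already provides it.
- **Wording:** reconcile the tolerance condition in Protocol 1.3.2 footnote o and 1.3.4 footnote c with E 13 and SAP 2. The same edit can settle whether the 4 hours run to ICF signing (1.3.4 footnote a) or to enrollment (footnotes o and c, E 13).

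The analyses use data already collected, so the cost is SAP text and a few tables. The restricted analyses will have fewer participants and wider intervals, and may differ by site practice, because pre-dosing follows local standard of care. They remove the selected subset from the estimate but cannot recover candidates who never enrolled.

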2 INTRODUCTION

Caplacizumab is a Nanobody® compound (NANOBODY® is a registered trademark of Sanofi or an affiliate) developed for the treatment of immune-mediated thrombotic thrombocytopenic purpura (iTTP), also known as acquired thrombotic thrombocytopenic purpura (aTTP), a life-threatening thrombotic microangiopathy manifested by formation of microthrombi in the microvasculature and consequent organ ischemia, hemolytic anemia, and severe thrombocytopenia. It is caused by inhibitory autoantibodies to von Willebrand factor (vWF) cleaving enzyme ADAMTS13, a disintegrin and metalloproteinase with a thrombospondin type 1 motif13, which results in a severe deficiency in the activity level of the enzyme.

Nanobodies are therapeutic proteins derived from the smallest functional fragments of heavy chain-only antibodies, which occur naturally in the Camelidae family (1). Caplacizumab consists of two identical humanized building blocks (PMP12A2hum1), linked by a 3-alanine linker and binds to the A1 domain of vWF and inhibits the interaction between vWF and platelets (5).

Caplacizumab is approved for the treatment of patients with aTTP (also known as iTTP), in conjunction with therapeutic plasma exchange (TPE) and immunosuppressive therapy (IST) at the following labeled dose(s) of 10 mg approved by the European Medicines Agency (EMA) and of 11 mg approved by the US FDA and Health Canada. Despite the difference in labelled doses, the formulations approved in both regions are identical and yield the same average dose of 10 mg.

2.1 STUDY RATIONALE

Caplacizumab is currently indicated for the treatment of patients with aTTP (also known as iTTP), in combination with TPE and IST. Although TPE has been considered a mainstay of iTTP treatment for several decades, it is a burdensome and invasive procedure for patients, and is associated with significant complications, and a substantial number of patients remains at risk for morbidity and mortality when treated with TPE and immunosuppression alone. Based on pathophysiology of iTTP and mechanism of action of caplacizumab, it is hypothesized that caplacizumab and immunosuppression without initial TPE may be safe and effective as first-line therapy for iTTP. This concept is supported by pre-clinical data (1) as well as emerging real-world clinical evidence (2). Hence, the Sponsor is proposing an open-label, single-arm study to support the hypothesis that caplacizumab and IST can be effectively and safely administered to treat either first or recurrent iTTP episode in adults without first-line TPE, which would be added only if clinically indicated. A successful study will establish a new treatment paradigm and a new standard of care for treatment of iTTP for the use of caplacizumab and immunosuppression without first-line TPE.

2.2 BACKGROUND

Immune-mediated thrombotic thrombocytopenic purpura (also known as aTTP) is a life-threatening, thrombotic microangiopathy characterized by severe thrombocytopenia, microangiopathic hemolytic anemia, and organ ischemia. It is an ultra-orphan disease with an annual incidence reported to be about 3 cases per million people in the US (6, 7).

It is caused by inhibitory autoantibodies to vWF-cleaving enzyme ADAMTS13 that result in a severe deficiency in the activity level of the enzyme. Severe deficiency (<10%) of ADAMTS13 enzyme activity has been recognized as a biomarker specific for iTTP and is used in the acute and long-term management of patients with iTTP (8).

Von Willebrand factor, a key protein in hemostasis, plays a pivotal role in the recruitment of platelets to sites of vascular injury. More than 90% of circulating vWF is expressed by endothelial cells and secreted into the systemic circulation as ultra-large vWF (ULvWF) multimers. Under high shear stress conditions such as in arterioles and capillaries, the platelet-binding A1 domain of the ULvWF multimers interact spontaneously with the glycoprotein Ib-IX-V receptor on platelets. In healthy individuals, ULvWF multimers are immediately cleaved into smaller, regular-sized multimers by the vWF-cleaving protease ADAMTS13. This prevents ULvWF interaction with platelets and limits microthrombus formation. When there is severe ADAMTS13 deficiency, ULvWF released from the endothelium are not cleaved appropriately, leading to vWF-dependent platelet aggregation eventually resulting in microvascular thrombosis (9). The consumption of platelets in these microthrombi results in thrombocytopenia, one of the clinical feature of iTTP, and may present with muco-cutaneous bleeding symptoms such as epistaxis, bruising, petechiae, hematuria, and gastrointestinal bleeding (10, 11).

Prior to the availability of caplacizumab, episodes of iTTP were associated with an acute mortality of 10–20% and thromboembolic morbidities such as myocardial infarction and cerebrovascular accident. In addition, tissue ischemia caused by microvascular thrombosis may result in multiorgan dysfunction including renal dysfunction. Most patients have very high levels of lactate dehydrogenase (LDH) as a result of the combination of hemolysis and tissue ischemia. Elevations of serum troponin I and troponin T are common (12, 13).

The current standard of care for iTTP consist of a combination of TPE, IST and anti-vWF therapy (cicapacizumab) (4, 14). These treatments focus on the three major pathophysiological mechanisms in iTTP:

1. Therapeutic plasma exchange (TPE):

TPE, a procedure in which blood of the patient is passed through a medical device which separates out plasma from other components of blood and the patient's plasma is removed and replaced with a replacement solution such as colloid solution (eg, albumin and/or plasma) or a combination of crystalloid/colloid solution (15). Therapeutic plasma exchange replenishes the ADAMTS13 enzyme and removes anti-ADAMTS13 antibodies, and ULvWF multimers gradually from the circulation.

TPE is administered daily for the time needed to restore platelet counts to normal levels, which may take several days to weeks. Although the introduction of TPE treatment has substantially reduced mortality from around 90% to lower than 20%, in spite of greater

understanding of disease pathogenesis and the use of newer immunosuppressants, the mortality rate has not been further decreased until the availability of caplacizumab (12, 16, 17, 15, 18, 19, 20).

TPE is frequently associated with procedure and plasma-related complications. Reducing the duration of TPE, or eliminating TPE altogether, when possible, would therefore reduce the risk of patients experiencing these complications.

Complications of TPE

Although the introduction of TPE treatment has substantially reduced overall iTTP mortality from around 90% to lower than 20%, this therapeutic approach carries substantial morbidity and mortality risk in critically ill iTTP patients. Therapeutic plasma exchange related complications include procedural complications such as invasive catheter placement and associated AEs such as bleeding, thrombosis, infections, pneumothorax and plasma-related complications such as allergic reactions including anaphylaxis and serum sickness. Allergic reactions are more frequent due to large volumes of plasma required for the procedure. Fibrinogen levels may decrease after serial TPE procedures with cryoprecipitate depleted plasma as replacement (15).

Howard et al. reported 73 major complications related to TPE in 57 of 206 (28%) consecutive patients treated for clinically suspected TTP- hemolytic uremic syndrome (HUS) over 9 years. Five of 206 (2.4%) patients have died due to catheter-related complications (pulmonary hemorrhage, pneumothorax and systemic infection). Non-fatal catheter-related complications included systemic infections (documented bacteraemia, suspected bacteraemia, fungemia), thrombosis (catheter obstruction and venous obstruction requiring systemic anticoagulation therapy), pulmonary hemorrhage, retro peritoneal hemorrhage, pericardial tamponade and pneumothorax. Plasma related complications (all non-fatal) included hypotension requiring dopamine, anaphylaxis with cardiac arrest, hypoxia and vomiting (21).

Benhamou et al. reviewed data on all iTTP patients of the French reference Center for thrombotic microangiopathies registry prospectively enrolled through a 10-year period, between 2008 and 2018. They reported 48 venous thrombosis episodes in 314 patients with 378 iTTP episodes (12.7%) in those who received prolonged treatment with TPE. Venous thrombo-embolisms included catheter related thrombosis, deep venous thrombosis of extremities, pulmonary embolism, splanchnic vein thrombosis (22).

2. Immunosuppressive therapy:

Immunosuppressive therapy (corticosteroids and rituximab) addresses the formation of the neutralizing ADAMTS13 autoantibodies, ultimately resulting in a gradual restoration of ADAMTS13 activity over a period of days to weeks. Once ADAMTS13 activity levels have stably normalized, normal processing of ULvWF will occur and the underlying autoimmune component of the disease is considered resolved.

Importantly, neither TPE nor immunosuppression directly address the pathophysiological platelet aggregation that leads to the formation of the microthrombi, and, in cases of inadequate response and unresolved disease, patients may experience exacerbations after stopping TPE. Also, as neither TPE nor IST have an immediate onset, patients remain at

risk for microthrombotic damage and ensuing clinical consequences during the time needed for these treatments to take effect.

3. Anti-vWF Therapy (Cplacizumab)

Cplacizumab (Cablivi[®]) is a bivalent Nanobody compound of approximately 28 kDa in size. Cplacizumab binds to the A1 domain of vWF and specifically inhibits the interaction between vWF and platelets, thereby immediately preventing the platelet adhesion and microthrombi formation leading to the clinical consequences of the disease. In this way it prevents the patient from further microthrombotic damage during the time needed for TPE and immunosuppression to take effect (5).

A detailed description of the chemistry, pharmacology, efficacy, and safety of cplacizumab is provided in the Investigator's Brochure.

